### 9.1.2. Definition of Serious Adverse Event (SAE)

A serious adverse event (SAE) is **ANY** event that meets one or more of the following criteria:

- Leads to a death
- Leads to a serious deterioration in the health of a subject that resulted in:
  - A life-threatening illness or injury
  - An injury or permanent impairment of a body structure or a body function

- In-patient hospitalization or prolongation of an existing hospitalization\*
- Medical or surgical intervention to prevent life-threatening illness or injury or permanent impairment to body structure or a body function
- Leads to fetal distress, fetal death or a congenital abnormality or birth defect.

\*Planned hospitalization for a condition present prior to the participant's enrollment in the study will not meet the definition of an SAE. An AE would meet the criterion of "hospitalization" if the event necessitated an admission to a health care facility (e.g., an overnight stay). Emergency room (ER) visits that do not result in admission to the hospital should be evaluated for one of the other serious outcomes.

### 9.1.3. Adverse Device Effect (ADE) / Serious Adverse Device Effect (SADE)

An Adverse Device Effect (ADE) is an adverse event related to the use of the device under study.

NOTE 1: This includes any adverse event resulting from insufficiencies or inadequacies in the instructions for use, the deployment, the implantation, the installation, the operation, or any malfunction of the medical device under study.

NOTE 2: This includes any event that is a result of a use error or intentional abnormal use of the investigational device under study.

A **Serious Adverse Device Effects (SADE)** is an adverse device effect that has resulted in any of the consequences characteristic of an SAE.

#### 9.1.4. Unanticipated (Serious) Adverse Device Effect (UADE/USADE)

An **unanticipated adverse device effect (UADE)** or **unanticipated serious adverse device effect (USADE)** is any serious adverse effect on health, safety, any life-threatening problem, or death caused by, or associated with a device, if that effect, problem, or death was not previously identified in nature, severity, or degree of incidence in the post market clinical follow up plan or risk analysis report, or any other unanticipated serious problem associated with a device that relates to rights, safety, or welfare of subjects.

Refer to Table 8 for a comprehensive list of foreseeable and anticipated adverse events.

#### 9.1.5. Study Device Deficiency, Failure or Malfunction

A device has failed if it does not perform according to the IFU or fails to meet the expectations of the device and/or investigator (i.e., related to appearance of the device, performance, durability, safety, effectiveness, quality, reliability, labeling, etc.). If a device failure is detected or suspected, it should be documented on the appropriate eCRF and device failure and AE must be reported as soon as possible to the Sponsor per section 9.4.

### 9.2. Classification of an Adverse Event

### 9.2.1. Severity of Event

The intensity or severity of each AE must be assessed according to the following classifications:

Mild	Awareness of signs, symptoms, or events that are otherwise easily tolerated that may result in minimal transient impairment of a body function or damage to a
IVIIIG	
	body structure, but do not require intervention other than monitoring.
	Any event that results in moderate transient impairment of a body function or
Moderate	damage to a body structure that causes interference with usual activities, or that
Woderate	warrants possible intervention, such as the administration of medication, to
	prevent permanent impairment of a body function or damage to a body structure.
	Any event that is incapacitating (an inability to do usual activities) or is life-
Source	threatening and results in permanent impairment of a body function or damage
Severe	to a body structure, or requires intervention, such as major surgery, to prevent
	permanent impairment of a body function or damage to a body structure.

#### Table 5. Intensity or Severity Definitions

### 9.2.2. Relationship to Study Device

For all collected AEs, the clinician who examines and evaluates the participant will determine the AE's causality based on temporal relationship and his/her clinical judgment. The degree of certainty about causality will be graded using the categories below.

Caused By	Relationship	Definition of Relation
	Causal	The event is associated with the device under study beyond reasonable doubt
	Probable	The relationship with the use of the device under study seems relevant and/or the event cannot reasonably explained by another cause, but additional information may be obtained
Device	Possibly	The relationship with the use of the device under study is weak but cannot be ruled out completely
	Unlikely	The relationship with the use of the device under study seems not relevant and/or the event can be reasonably explained by another cause, but additional information may be obtained
Not Related		Relationship to the device under study can be excluded
Causal		The event is associated with the study procedure beyond reasonable doubt
Chudu	Probable	The relationship with the study procedure seems relevant and/or the event cannot be reasonably explained by another cause, but additional information may be obtained
Study Procedure	Possibly	The relationship with the study procedure is weak but cannot be ruled out completely
	Unlikely	The relationship to the study procedure seems not relevant and/or the event can be reasonably explained by another cause, but additional information may be obtained
	Not Related	Relationship to the procedure can be excluded

### 9.2.3. Outcome

The outcome of each AE must be assessed according to the following classifications:

Classification		Definition	
Recovered	Resolved	Subject fully recovered with no observable residual effects	
Recovered	Resolved with sequelae	Subject recovered with observable residual effects	
Recovering	Resolving	Adverse event has not resolved and additional change in condition is possible	
Not Recovered	Not Resolved	Subject didn't recover from the AE and the observed AE effects are still present	
Fatal		Subject died as a result of the AE (whether or not the AE is related to the device or procedure)	

### 9.2.4. Anticipated Adverse Event

An anticipated Adverse Event is an effect which by nature, incidence, severity or outcome has been identified as a possible complication associated with the investigational medical device and/or intervention procedure.

Potential adverse events that are reasonably anticipated to occur during the cardiac electrophysiology procedure are listed in Table 8. These events should be reported via EDC as anticipated AEs.

#### **Table 8. Comprehensive List of Anticipated AEs**

Anticipated Adverse Events	
Acute Respiratory Distress Syndrome (ARDS)	Air embolism
Allergic reaction	Allergic reaction to Anesthesia (e.g., hair loss)
Anaphylactic shock	Anemia
Anesthesia reaction	Apnea - sedation induced
Arrhythmia: bradycardia	Arrhythmia: pro-arrhythmias
Arrhythmia: tachycardia	Aspiration pneumonia
Asthmatic attack	Atelectasis
Atelectasis	Atrial fibrillation*
Atrio-Esophageal fistula	Atypical left atrial flutter
AV fistula	Bleeding complications
Bleeding requiring transfusion	Cardiac arrest
Cardiac perforation	Cardiac thrombo-embolism
Cerebro-vascular accident (CVA) / stroke	Chest pain/discomfort
Complete heart block, temporary or permanent	Conduction block: ongoing / resolved

Congestive Heart Failure	Coronary artery dissection
Coronary artery occlusion	Coronary artery spasm
Coronary artery Thrombosis	Damage to the vascular system
Death	Deep venous thrombosis
Diaphragmatic paralysis	Dislodgement of permanent pacing leads
Disseminated Intravascular Coagulation	Dyspnoea
Endocarditis	Epistaxis
Esophageal Injury	Exacerbation of pre-existing
	arrhythmia*
Expressive aphasia	Fainting
Fatigue	Gastric reflux
Gastrointestinal diverticulosis	Gastro-intestinal NOS
Heart Failure	Hematoma (local) /ecchymosis
Hemorrhage	Hemothorax
High / increased creatine phosphokinase	Hypotension
(СРК)	
Нурохіа	Increase in frequency or duration of
	episodes of typical atrial flutter
Increased phosphokinase level	Infection, localized
Infection, systemic	Injury to skin, muscle, connective tissu
	due to body position, electrical
	cardioversion, etc.
Laceration	Leakage of air or blood into the lungs
	or other organs due to perforation
Liver toxicity	Mobile strands in Inferior Vena Cava
Myocardial Infarction	Nausea
Neurological disorders (headache)	Neurological disorders (poor
	coordination)
Neurological disorders (tremor)	Obstruction to the vascular system
Palpitations	Perforation to the vascular system
Pericardial effusion without tamponade	Pericardial effusion resulting in
	tamponade
Peripheral embolus	Pericarditis
Peripheral thromboembolism	Peripheral nerve injury
Phrenic nerve damage	Phlebitis
Pneumothorax	Pleural effusion
Pulmonary edema	Pseudoaneurysm
Pulmonary hypertension	Pulmonary embolism
Pulmonary vein dissection	Pulmonary toxicity, like acute
	pulmonary syndrome
Pulmonary vein thrombus	Pulmonary vein Stenosis
Renal failure	Pump failure
Respiratory failure	Respiratory depression
Rhabdomyolysis, including produced by	Retroperitoneal hematoma
body position or propofol	
Seizure	Sedation induced CO 2 retention with
	lethargy and cholecystitis
Skin burns (due to cardioversion, tape, etc)	Sepsis

Skin injury / muscle or connective tissue injury due to body position, electrical cardioversion	Skin discoloration
Tamponade	Skin rash
Thrombocytopenia	Temperature elevation
Thrombosis	Thromboembolism
Transient extremity numbness	Thyroid disorders
Unintended complete or incomplete AV,	Transient ischemic attack (TIA)
Sinus node, or other heart block or damage	
Urinary tract injury or infection related to	Urinary retention
the urinary catheter	
Vasovagal reactions	Valvular damage/insufficiency
Volume overload	Vision change
X-ray radiation injury of skin, muscle and/or	Worsening obstructive, restrictive, or
organ	other form of pulmonary disease

\*Atrial Fibrillation and exacerbation of an existing arrhythmia are anticipated adverse events. However, they will not be captured as such under this protocol, as they are considered recurrence of disease.

## 9.3. Time Period and Frequency for Event Assessment and Follow-up

The investigator, or designated individual, will record all reportable events with start dates occurring any time after informed consent is obtained. At each study visit, the investigator will inquire about the occurrence of AE/SAEs since the last visit.

All AE/SAEs need to be followed until the event is resolved (with or without sequelae). The medical monitor or designee of this clinical investigation will decide if more follow up information is needed in case the event is not resolved at study completion. All required treatments and outcomes of the (S)AE must be recorded in the eCRF. Additional documentation may be requested by the Sponsor or designee, including but not limited to, a written subject narrative detailing the clinical course of the AE/incident, a copy of any correspondence with the local REB, hospital records, death certificate and autopsy report if available. The local CHU will collect the resolution information of any reported SAEs.

### 9.4. Reporting Procedures

### 9.4.1. Adverse Event Documentation and Reporting Requirements

Subjects should be encouraged to report AEs spontaneously or in response to general, nondirected questioning (e.g. "How was your health been since last visit?"). Anytime during the study, the subject may volunteer information that resembles an AE.

Each AE must be reported to the sponsor regardless of classification, seriousness, intensity, outcome or causality. The investigator is responsible for ensuring that all AEs observed by the investigator, or reported by the subject, that occur from the time that the subject has signed the informed consent through the end of the study are properly assessed, recorded, and reported as defined and described in the AEs, Adverse Device Effects and Device Deficiencies section of this protocol. All adverse events must be documented by completing subject's medical records (source documents) and appropriate eCRF by the investigator or study coordinator throughout

the study and provided to the Sponsor. All AEs will be monitored until they are adequately resolved or explained.

Anonymized documentation pertaining to the AE (e.g. laboratory tests, consultation reports, postmortem reports, new information relating to a previously reported AE, correspondence with the local EC, etc.) will be provided by the investigator to the sponsor or designee in a timely manner, when requested. Follow-up reports relative to the subject's subsequent course must be submitted to the sponsor or designee until the event has resolved or, in case of permanent impairment, until the condition stabilizes. If the subject is withdrawn from the study because of the AE, the information must be included on the appropriate eCRFs.

The sponsor is responsible for the classification of AEs and ongoing safety evaluation of the study and shall review the investigator's assessment of all AEs. The sponsor will determine and document in writing their seriousness and relationship to the investigational device. In case of disagreement between the sponsor and the principal investigator(s), the sponsor shall communicate both opinions to the concerned parties.

Biosense Webster will ensure that investigators are instructed to return devices suspected of causing an AE or SAE (i.e., definitely device-related or possibly device-related) in accordance with relevant regulations and current company procedures.

In the case of serious device effects and device deficiencies that could have led to serious adverse device effects, the Sponsor will determine whether the risk analysis needs to be updated and whether corrective or preventative action is required.

Timing for reporting the different types of AEs is described in Table 9.

Type of Adverse Event	Reporting Requirements
Serious Adverse Events	Report to Sponsor immediately upon awareness of event but no later than 72 hours
USADE & SADE	Report to Sponsor immediately upon awareness of event but no later than 72 hours
Primary AEs	Report to Sponsor immediately upon awareness of event but no later than 72 hours
Study device failure/malfunction associated with an AE	Report both study device failure and AE to Sponsor immediately upon awareness of event but no later than 72 hours
All other Adverse Events	Report to Sponsor within 2 weeks upon awareness of the event

#### Table 9. AE Reporting Requirements

### 9.4.2. Incident Reporting

All Adverse Event will be reviewed by the Complaint Handling Unit (CHU) of the Sponsor, where the assessment will be made if the respective event is reportable as required by Health Canada.

The sponsor will submit as per site specific requirements in a timely manner to all participating clinical investigators, a safety overview. Pursuant to EN ISO 14155AEs will be fully

recorded and reported by the sponsor to Health Canada as well as the REB according to the requirements and deadlines in force.

### 9.4.3. Events of Special Interest

Event reporting to Health Canada in accordance with the jurisdictional regulations will occur by the sponsor and/or by the investigator, depending upon the local requirements.

A device deficiency related to a medical device not manufactured by Biosense Webster should be reported by the investigator to their respective manufacturer as per relevant regulation. Complaints related to non-Biosense Webster, Inc. products must be handled according to institutional policies, HC policies, and local regulations.

## 9.5. Safety Oversight

Safety oversight will be conducted by the Medical Safety group. Aggregate safety data will be reviewed during enrollment by the study safety lead in order to promptly identify new issues or trends which may have an impact on the conduct of the study and/or subject safety. As deemed applicable, under the rules of an approved study-specific charter, safety events might be reviewed by an established committee which may recommend appropriate action(s) to ensure subject safety.

## **10.** Administrative Responsibilities

## **10.1. Ethics Committee and Competent Authority Application**

The study protocol (or amendment[s]), ICF, and other applicable study related documents must be approved by HC before enrollment of subjects. Any additional requirement imposed by the EC or regulatory authority shall be discussed, agreed upon, and followed. A signed copy of the EC and CA (if applicable) approval letters addressed to the investigator must be submitted to Biosense Webster certifying study approval prior to subject enrollment. Biosense Webster and the EC must approve, in writing, any changes to the protocol that affect the rights safety and/or welfare of the subjects, or may adversely affect the validity of the study.

### 10.2. Audits and Inspections

The sponsor and/or designee and/or Regulatory Authorities may contact the participating institution to inform the investigator of an upcoming audit/inspection. The investigator should immediately notify the sponsor of any Regulatory Authority audits/inspection at the study site. The audit/inspection can include the review of documents, facilities, records and any other resources deemed by the authorities to be related to study.

## **11.** Deviations from the Clinical Study Plan

The investigator is responsible for ensuring that the clinical investigation is conducted in accordance with the procedures and evaluations described in this protocol. The study monitors shall verify that the conduct of the study is in compliance with the currently approved protocol and applicable regulations, and shall identify any issues of non-compliance with regulations or guidelines.

Issues of non-compliance include but are not limited to repeated protocol deviations; failure to obtain proper informed consent; non-conformance to EC requirements; failure to report Adverse Events, product malfunctions and other product issues; and other non-conformance to GCPs.

A protocol deviation is defined as an instance of failure to follow, intentionally or unintentionally, the requirements of the protocol (e.g. missed test or procedure, visit out of window, non-adherence to inclusion/exclusion criteria). Investigators are not allowed to deviate from the protocol. Protocol deviations will be monitored closely and will be reported per EC/CA requirement.

Under emergency circumstances, deviations from the protocol to protect the rights, safety and well-being of a subject may proceed without prior approval of the sponsor and EC. Such deviations shall be documented and reported to the sponsor and the EC as required.

All instructions described in this study protocol are to be followed. If an amendment is required, it must be made in written form and receive approval from all persons and authorities who approved the original protocol. Administrative changes (do not affect subject's benefits/risks ratio) may be inserted with abbreviated approval. All amendments will be distributed to all original protocol recipients.

# **12.** Investigational Product Accountability

## **13.** Clinical Monitoring

Clinical site/remote (targeted) monitoring is conducted to ensure that the rights and well-being of human subjects are protected, that the reported trial data are accurate, complete, and verifiable, and that the conduct of the trial is in compliance with the currently approved protocol/amendment(s), with GCP, and with applicable regulatory requirement(s). Each site might undergo periodic monitoring of the study, which might involve a visit from a Sponsor representative, qualified to perform such visit.

Monitoring contacts (visits or remote) may include, but are not limited to, the following:

- Protocol adherence
- Source documentation verification and accuracy of the eCRFs
- Verification that informed consent is being obtained for all subjects participating in the study in accordance with requirements described in the study protocol
- Verification of completeness of the Site File
- Verification of accuracy of all study logs such as the Delegation of Responsibility Log, etc.
- Compliance with applicable regulations
- Identification and action to resolve any issues or problems with the study.

Data are to be submitted promptly via e-CRF after collection. Missing or unclear data will be corrected as necessary throughout the trial. Biosense Webster will request further documentation such as physician and/or cardiac EP lab procedure notes when complications or malfunctions are observed and reported.

Further details on clinical monitoring are provided in the study specific monitoring plan.

## **14.** Statistical Methodology

The Sponsor will be responsible for the overall analysis of data from this protocol. This section represents the Statistical Analysis Plan for this protocol. All analyses and subsequent detail are described below.

## 14.1. Levels of Significance

All data will be summarized by descriptive analyses. No formal statistical inference will be made.

## 14.2. Analysis Sets

The following analysis populations will be used to complete the analyses of data:

- **Safety Analysis Set**: The Safety Analysis Set will include all enrolled subjects who have the investigational device inserted, regardless if RF energy is delivered.
- Effectiveness Analysis Set : The effectiveness analysis set will include all enrolled subjects who meet the study eligibility criteria, have the investigational device inserted and undergo an ablation procedure with the study catheter used in conjunction with QMODE+ and /or QMODE for PVI (RF energy is delivered). The subjects without any QMODE+ applications for PVI will be considered a failure.

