	The QDOT-nGEN study is a prospective, multi-center, non-randomized, interventional clinical workflow study.						

Sample Size and Statistical Analysis	Up to 50 subjects with a minimum of 30 subjects undergoing a study ablation						
Statistical Analysis	procedure will be enrolled.						
	This study is a workflow study, there is no statistical power calculation and no						
	hypothesis will be tested. Descriptive statistics will be presented. Thirty subjects (30) undergoing an ablation procedure are deemed enough to characterize safety and						
	acute performance.						
Study Population	Subjects with AF who are scheduled to undergo a clinically indicated ablation						
	procedure for management of their AF will be the target population for screening						
Geographic areas to be included	e Up to 6 centers in Canada						
Study Duration	Approximately 9 months						
Participant Duration	Subjects will be followed until completion of the 3-month visit post-procedure						
Procedure Description	Subjects will arrive to the electrophysiology laboratory for their ablation procedure and will undergo preparation for the procedure per the hospital's standard protocol (discretion of investigator).						
	The AF Ablation procedure will follow below sequence:						
	
 
Esophageal monitoring to avoid injury is recommended when ablating near the esophagus
 
						
	Anatomical mapping of the left atrium						
	Introduction of the study catheter						
	
 
Circumferential Pulmonary Vein Isolation (PVI) primarily using QMODE+ mode
 
						
	
 
Confirmation of PVI with Lasso® or PentaRay® (or other at investigators discretion)
 
						
	Confirmation of entrance block with adenosine/isoproterenol challenge						
	In this study protocol, QMODE+ is to be used as the primary mode for pulmonary v isolation. Only after the investigator deems QMODE+ is unable to achieve PVI sho the study catheter in QMODE be used to complete the procedure.						
	Additional RF ablation lesion outside the PVs can be made by either QMODE+ or QMODE at the discretion of the physician.						
Primary Endpoints	Acute Performance:						
	Acute Procedural Success defined as confirmation of entrance block in all targeted PVs after adenosine and/or isoproterenol challenge using the nGEN / QDOT Micro Ablation System						
Additional Data	Adverse events:						

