# 3.2. Study Endpoints

#### 3.2.1. **Primary Endpoint(s)**

The primary endpoint is to confirm pulmonary vein isolation. This is defined as confirmation of entrance block in all targeted PVs after adenosine and/or isoproterenol challenge using the nGEN/ QDOT Micro Ablation System.

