## 4.5. Subject Enrollment Disposition

The following subject groups are defined:

- Enrolled Subjects: Patients who sign the informed consent form.
- Excluded Subjects: Subjects who are enrolled but never undergo insertion of the study catheter.
- **Discontinued Subjects**: Enrolled subjects who have the study catheter inserted but do not undergo ablation (no RF energy is delivered with the study catheter and the nGEN generator).

- Lost to Follow-up Subjects: Subjects for whom contact is lost after most recent visit (despite 3 documented attempts to contact the subject).
- Withdrawn / Early Termination Subjects: Subjects who withdraw consent for study participation or are withdrawn by the investigator, are terminated from the study prior to completion of all follow-up visits.
- **Completed Subjects:** Enrolled subjects who have not been excluded, discontinued, expired, withdrawn, terminated early, or lost-to-follow-up from the study prior to the final study visit.

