### 14.3. Sample Size Justification

Since this study is a workflow study with no primary hypotheses to be tested, there are no statistical power calculations. Evidence from between 30 to 50 prospectively enrolled subjects are deemed sufficient to characterize safety and performance of the Qdot-nGen ablation system.

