#### 14.4.4. Analysis for Primary Endpoint

Acute procedural success will be summarized using categorical summaries for the effectiveness analysis set.

A listing of the primary endpoint will be provided.

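### Acute success is reported only in subjects who received RF, so an eligible, catheter-inserted subject with no RF because the generator or system failed leaves the denominator instead of counting as a failure

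*Combined protocol and SAP*

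**What the plan says.** Section 14.2 defines two sets. The Safety Analysis Set takes "all enrolled subjects who have the investigational device inserted, regardless if RF energy is delivered". The Effectiveness Analysis Set requires eligibility, device insertion and, in addition, that subjects "undergo an ablation procedure with the study catheter used in conjunction with QMODE+ and /or QMODE for PVI (RF energy is delivered"). A further sentence in that definition counts subjects with no QMODE+ application for PVI as failures.

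Section 14.4.4 uses only the second set: "Acute procedural success will be summarized using categorical summaries for the effectiveness analysis set". Section 4.5 classes as Discontinued those who have the catheter inserted but "do not undergo ablation (no RF energy is delivered with the study catheter and the nGEN generator"). It makes no distinction by cause.

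The primary endpoint in section 3.2.1 is "confirmation of entrance block in all targeted PVs after adenosine and/or isoproterenol challenge using the nGEN/ QDOT Micro Ablation System". Section 14.3 says that 30 to 50 subjects are "deemed sufficient to characterize safety and performance of the Qdot-nGen ablation system". The equipment table in section 6.7 lists the nGEN Generator as the only investigational item, and section 1.2.1 explains that its upgraded version is not licensed in Canada.

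**The concern.** The generator's listed function is to send RF energy to the catheter. If it fails to do so in a subject whose catheter is already in place, the system under study has failed in the most basic way. Under the present sets that subject is not a failure of acute success; the subject is simply absent from the rate.

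The result is also uneven. A subject isolated with QMODE alone is scored as a failure, while a subject in whom the system delivered no energy is not scored. The planned check of RF delivery from the generator logs does not fill the gap, because section 14.4.5 places it in the effectiveness set, where RF delivery is already a condition of entry.

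What is at stake is the meaning of the headline rate. It describes performance given that RF was delivered, and it would be too high if read as performance of the system.

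**Working it through.** **Where the subject goes.** I read device insertion in section 14.2 as catheter insertion, since a generator is not inserted. Take an eligible subject with the catheter inserted and no RF because of a generator fault.

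1. Section 4.5: Discontinued.
2. Section 14.2, safety set: included, since RF is not required.
3. Section 14.2, effectiveness set: not included, since RF for PVI is required.
4. The rule on absent QMODE+ applications is written within the effectiveness-set definition. It therefore reaches members of that set, such as a subject isolated with QMODE only, and does not bring this subject back.
5. Section 14.4.4: acute success is summarised on the effectiveness set, so the subject is in neither numerator nor denominator.

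Changing the set alone would not be enough. Section 14.4.1 bases percentages on non-missing data and section 14.4.7 rules out imputation. A subject with no entrance-block assessment could drop out again unless the text says that this outcome is a failure.

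**Size.** The plan has no target rate, test or threshold, and no rate of device-caused absence of RF, so there is no figure to reproduce. Let N be the eligible, catheter-inserted subjects and k those with no RF for a device reason. Assume k from 0 to 3, no other no-RF subjects, and every treated subject isolated.

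- As planned: (N − k)/(N − k) = 100% for every k.
- With the k cases as failures: (N − k)/N.

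N = 33 is the smallest N that still leaves the minimum of 30 ablated when k = 3. N = 50 is the planned maximum.

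| k | Planned | N = 33 | N = 50 |
|---|---|---|---|
| 0 | 100% | 33/33 = 100% | 50/50 = 100% |
| 1 | 100% | 32/33 = 97.0% | 49/50 = 98.0% |
| 2 | 100% | 31/33 = 93.9% | 48/50 = 96.0% |
| 3 | 100% | 30/33 = 90.9% | 47/50 = 94.0% |

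Each case costs 1/33 = 3.0 points or 1/50 = 2.0 points.

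**One treated failure as well (k = 1).** N = 33: 31/32 = 96.9% planned against 31/33 = 93.9%, a loss of 2.9 points. N = 50: 48/49 = 98.0% against 48/50 = 96.0%, a loss of 2.0 points. The loss per case hardly changes.

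**Effect of attribution.** Suppose one no-RF case is due to the device and one is not, with all treated subjects isolated.

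| Rate | N = 33 | N = 50 |
|---|---|---|
| Planned | 31/31 = 100% | 48/48 = 100% |
| Device-caused no-RF as failure, the other case listed outside | 31/32 = 96.9% | 48/49 = 98.0% |
| Every no-RF subject as failure | 31/33 = 93.9% | 48/50 = 96.0% |

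The last two rows bracket the attribution judgement. No confidence intervals are given, because the plan makes no inference.

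**The case against.** The best case for the plan has four parts.

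- **The treated-only rate is a declared choice that fits the design.** The Protocol Summary counts its minimum in ablated subjects ("Up to 50 subjects with a minimum of 30 subjects undergoing a study ablation" procedure), and entrance block after a drug challenge presupposes an ablation. This stands, and it is why the planned rate should be kept. It does not make that rate a measure of the whole system.
- **The cases are not hidden.** Section 14.4.2 gives the size of both sets and discontinuations by primary reason, and section 14.4.6 lists device deficiencies. This also stands and limits the harm. A reader could rebuild the broader rate only in part, since the safety set may include ineligible subjects.
- **The QMODE+ failure sentence could be read to cover a subject with no RF at all.** The words fit, but the sentence sits inside a set that already demands RF. If the sponsor intended the wider reading, the definition conflicts with itself and still needs a clarifying sentence.
- **The size is assumed.** Nothing in the documents suggests that such failures are common, and k = 3 of 33 would be a 9% complete failure to deliver RF. A subject with any RF for PVI stays in the set and can fail. This is right: the figures show what each case would do, not what is expected.

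An inserted-subject rate is also still conditional, because a generator fault found before insertion lies outside it. The table should say so.

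**Conclusion.** The concern holds, as a minor point. Sections 4.5, 14.2 and 14.4.4 together remove an eligible, inserted subject with no RF from the only acute-success denominator, whatever the cause. If such cases occur, the reported rate overstates system performance by about 3.0 points per case at 33 inserted subjects and 2.0 points at 50. If none occur, there is no effect. No test, threshold or pass/fail decision changes.

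Confidence is high in the reading of the text and in the arithmetic. It does not extend to how often such cases will arise, on which the documents are silent.

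**What to change.** Keep the present RF-delivered analysis, and add the following to sections 14.2 and 14.4.4:

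1. Acute procedural success among eligible subjects with the study catheter inserted, counting no RF for a recorded device or system reason as a failure. State this as an outcome rule, so that the missing-data convention does not remove the subject.
2. A listing of inserted subjects with no RF for other reasons, with those reasons, outside this denominator.
3. Who makes the device/non-device attribution, and that it is fixed before database lock.
4. A bounding rate in which every eligible, inserted, no-RF subject is a failure.
5. A table footnote that a generator fault found before insertion makes the subject Excluded under section 4.5 ("Subjects who are enrolled but never undergo insertion of the study catheter") and so outside all three rates.
6. One sentence in section 14.2 saying whether the QMODE+ failure rule applies only within the effectiveness set.

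The cost is SAP wording, one attribution step in a study that the sponsor analyses itself (hence the pre-lock rule and the bound), and possibly a slightly lower success rate to report. New data collection is probably not needed: section 9.1.5 puts suspected device failures on the eCRF, section 4.4.2 records withdrawal reasons, and section 14.4.2 plans a summary by primary reason for discontinuation. The eCRF itself is not in the documents, so confirm that it captures the reason for no RF in Discontinued subjects.
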